**Table 1.**

Domain	Proposed measure (items)	Aims	Schedule	Participants
Demographic and Health Information	Age, sex, race, ethnicity, education level, perceived discrimination in healthcare encounters (FCP only), relationship to VNS Health Total member (FCP only), role on CBPC team (CBPC team members only), etc.	1-2	Baseline (Aim 1)	VNS Health Total members, FCP, CBPC team members, research/content experts (Aim 2 only)
	Age, sex, race, ethnicity, date of CBPC eligibility determination, date of CBPC refusal, diagnoses, triggering events	3	As extracted from electronic health record for pilot clinical trial analysis	VNS Health Total CBPC-eligible members
Knowledge of Palliative and Hospice Care	Palliative Care Knowledge Survey  additional questions on palliative care knowledge and attitudes 9/26/2025 8:41:00 PM	1-2	Baseline (Aim 1), following feedback on intervention materials (Aim 2)	VNS Health Total members, FCP
Intervention Development	Interview guides with questions about palliative care experiences, knowledge, barriers to participation in CBPC, including 5 rights framework (Aim 1); and user-centered design questions to solicit feedback on intervention materials (Aim 2)	1-2	1-time interview for Aim 1. 1-time think aloud session for Aim 2	VNS Health Total members, FCP, CBPC team members, research/content experts (Aim 2 only)
Intervention Feasibility and Acceptability	PC team member reports of use of intervention	3	1, 3, and 6 months into intervention delivery (Aim 3)	CBPC team members
	End-User Satisfaction Survey 	1, 3	Baseline (Aim 1); 1, 3, and 6 months into intervention delivery (Aim 3)	CBPC team members
Primary Endpoint	Number and rate of CBPC refusals (denominator=number of CBPC-eligible individuals)	3	As extracted from electronic health record for pilot clinical trial analysis	VNS Health Total CBPC-eligible members

**Data Collection Protocol.** Survey responses for Aims 1-3 will be collected in two ways: online or by telephone. Whenever possible, participants will be sent surveys to their preferred emails via REDCap, a password protected, HIPAA compliant data management system. Survey links will be unique to study

participants. If participants prefer to provide answers to survey questions over the phone or provide incomplete information in the online format, research staff will call the participant at the participant's preferred phone number to ask the questions. The research staff will record participants' answers in REDCap. Interviews and focus groups for Aims 1 and 2 will be conducted by phone or secure videoconference (e.g., Zoom, Teams). For videoconferences, study participants will be sent an encrypted link to their preferred email. Rutgers requires all Zoom users to use secure, up-to-date versions of the software. Zoom meetings cannot be accessed without the personalized link study staff will provide. Study team members have experience with or will be trained in obtaining answers to survey questions by phone and conducting interviews and focus groups by phone and videoconference (e.g., Zoom) including conducting the phone calls in a private area to protect participant confidentiality.

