### 2. SPECIFIC AIMS.

The specific Aims of the study are:

**Aim 1:** Engage FCPs and CBPC team members to identify barriers to CBPC. Aim 1 will incorporate the perspectives of 10 CBPC team members and 25 VNS Health Total members and FCPs of PLwD and those with other diagnoses who refused CBPC services.

**Aim 2:** Develop informational materials for CBPC team members to use when speaking with patients and FCPs about CBPC and process for tailoring information delivery based on patient's algorithm-identified risk profile. 10-15 persons from interested parties (CBPC team members, FCPs, content/research experts) will provide feedback on intervention materials. Most participants will be recruited from Aim 1 participants. Additional participants will be recruited as necessary.

**Aim 3:** Conduct a pre-post trial to determine the feasibility and acceptability of the materials and using them in existing clinical workflows for their 1) impact on CBPC enrollment for CBPC-eligible individuals, including PLwD, and 2) end-user satisfaction.

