### 3. STUDY DESIGN

The study proposes to identify barriers to CBPC enrollment and develop ways to use the information from a valid, accurate data-drive algorithm to address barriers to enrollment. The study will 1) develop informational materials for CBPC team members that can be used to explain CBPC in a manner tailored to a patient's algorithm-identified risk profile (the intervention), and 2) pilot test whether the informational materials have an impact on CBPC uptake among patients who previously refused CBPC. This study will use a multi-methods design including data collection and pilot testing.

To achieve **Aim 1** focus groups and interviews with CBPC team members, VNS Health Total members, and FCP will be conducted to identify items important in accepting and refusing CBPC.

For **Aim 2** we will develop the intervention. The intervention is a set of information materials that address CBPC generally and challenges that CBPC can help manage. The materials will be tailored to patient needs based on their algorithm identified risk profile (e.g., disease progression, medication, and symptom management). The materials will be used by CBPC team members when introducing and describing the CBPC program to VNS Health Total members and FCP.

Aims 1 and 2 participants will not be offered any services. They will be asked about their understanding of palliative and why they chose not to accept it in the past. Their responses will be used to improve how palliative care services and programs are explained to others in the future.

For **Aim 3** we will compare intervention and usual care CBPC refusal rates and assess CBPC team member and FCP satisfaction with intervention materials using the End-User Satisfaction Tool. Because of the size of the CBPC clinical team and workflow structure, it is not feasible to randomize CBPC team members to intervention or control groups. As such, we will use a pre-post pilot clinical trial to test the feasibility and efficacy of the informational materials and process, compared to usual practice, on CBPC refusal rates. We will retrospectively examine CBPC refusal rates (CBPC refusals/CBPC eligible individuals) for a 6-month lookback

period prior to implementing the intervention (informational materials and process). We will compare this rate of refusal to the CBPC refusal rate for a 6-month period after implementing the intervention.

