### **Aim 3. Conduct a pre-post trial to determine the feasibility and acceptability of the materials and using them in existing clinical workflows for their impact on CBPC enrollment for PLwD and end-user satisfaction.**

*Sample.* Based on 2022 identification, eligibility, and refusal data, we anticipate 500 VNS Health Total members will be identified as eligible for CBPC during the study period (250 control, 250 intervention) and that

80 individuals will refuse CBPC during the pre-test/control period. Of these, 365 CBPC-eligible and 60 refusals are expected to be PLwD.

*Inclusion Criteria.* All VNS Health Total members who were identified as eligible for CBPC in the 6-month period prior to the introduction of the intervention (tailored informational materials about benefits of palliative care) and in the 6-month period following the introduction of the intervention.

*Exclusion Criteria.* VNS Health Total members who were not identified as potentially eligible for CBPC services by the 12-month mortality risk algorithm or who were identified by the algorithm as potentially eligible for CBPC services but determined by the clinical team to be ineligible for CBPC. At times, individuals are flagged by the algorithm as potentially eligible for CBPC, but upon further assessment by the palliative care team, it is determined that CBPC is not appropriate at this time. For example, someone may be flagged because they are over 90 years old and recently visited the emergency department. However, upon further assessment, the clinical team determines that they are highly functional and independent, their chronic conditions are well-managed, and the emergency room visit was for a minor head wound or something similar that did not greatly impact the individual's functional or health status.

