## **7. REQUEST FOR WAIVER OF AUTHORIZATION**

In addition to obtaining consent from FCP, CBPC team member and research/content expert participants, we are requesting a waiver of consent and HIPAA authorization to access VNS Health Total member electronic records for the following reasons.

**Planning.** We will extract information about refusals of CBPC in the electronic health record such as the number of individuals who refused CBPC, their demographics, and health information (e.g., key diagnoses, triggering events that made them eligible for CBPC). Analyzing this information will allow us to improve information about risk for CBPC and who is refusing services so that we can create information materials and process 1) to support CBPC enrollment, particularly for PLwD and 2) that can be tested in other healthcare settings. As this extraction will involve several hundred records, including for deceased individuals, it is not possible to obtain this information without a waiver of authorization.

**Aims 1-2.** We request the waiver for VNS Health study staff to view electronic records of VNS Health Total members to identify VNS Health Total members and FCP who are potentially eligible to participate in Aims 1 and 2 of the study. It is not possible to identify potentially eligible members or FCP without the waiver of authorization.

**Aim 3.** We request the waiver for VNS Health study staff to view identification, enrollment, and refusal data. The information will be used to calculate CBPC refusal rates before and after intervention delivery and to analyze factors associated with CBPC enrollment and refusal in multivariable statistical modeling (described below).

A Request for Waiver of Authorization Form is included in the appendix of this application.

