### **Quantitative Analysis.**

For Aim 3, based on 2022 identification, eligibility, and refusal data, we anticipate 500 individuals will be identified as eligible for CBPC during the study period (250 control, 250 intervention) and that 80 individuals will refuse CBPC during the pre-test/control period. Of these, 365 CBPC-eligible and 60 refusals are expected to be PLwD.

We will use descriptive statistics to describe the sample. End-user satisfaction results will be reported as mean ratings for each item and across all items as a composite score. Results will also be reported by percentages of respondents by Likert scale level, as well as grouped by percent favorable and unfavorable. Percentage of clinicians finding the intervention to be feasible and acceptable and the proportion reporting using the informational materials will be calculated.

Additionally, we will determine the association between the intervention and reductions in refusal of CBPC among eligible individuals. We will use a pre/post design for this pilot clinical trial. For the pre-intervention measurement, we will calculate the number of palliative care services refusals among all palliative care-eligible VNS Health Total members (expected n=250) for a 6-month lookback period prior to introducing the informational materials into clinical practice. For the post-intervention measurement, after incorporating the informational materials into clinical practice, we will observe palliative care refusals prospectively for 6 months among all palliative care-eligible VNS Health Total members (expected n=250). We hypothesize that the number of refusals will decrease during the 6-month intervention period.

We assume we will see approximately 80 refusals among the 250 pre-intervention patients, for a refusal rate of  $80/250 = 0.32$  (or 32%) or  $H_0 = p_{pre} \geq p_{post}$ , where  $p_{pre}$  and  $p_{post}$  are the pre and post intervention CBPC refusal rates, respectively.

The table below show the post-intervention CBPC refusal rates we will be able to detect, for different power levels, assuming a total of 500 patients (250 pre, 250 post) a significance level  $\alpha = 0.05$ , and a pre-intervention CBPC refusal rate of 0.32.

Power	Pre-intervention CBPC refusal rate	Post-intervention CBPC refusal rate	Absolute rate reduction	Percent rate reduction
0.80	0.32	0.206	0.114	35.6%
0.85	0.32	0.199	0.121	37.8%
0.90	0.32	0.190	0.130	40.6%
0.95	0.32	0.178	0.142	44.4%

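### Aim 3 asks about impact on CBPC enrollment, but the plan compares only the refusal rate, and nothing says that members who do not refuse enroll

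*Combined protocol and SAP*

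**What the plan says.** **The aim.** Section 2 states Aim 3 in terms of "impact on CBPC enrollment for CBPC-eligible individuals, including PLwD". The Aim 3 heading in Section 4 has "impact on CBPC enrollment for PLwD and end-user satisfaction", and the Aim 3 paragraph of Section 10 repeats enrollment.

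**The outcome.** The primary endpoint in Table 1 is "Number and rate of CBPC refusals (denominator=number of CBPC-eligible individuals". Section 3 describes the comparison: "We will compare this rate of refusal to the CBPC refusal rate for a 6-month period after implementing the intervention". Section 9, Quantitative Analysis, gives the hypothesis, "We hypothesize that the number of refusals will decrease during the 6-month intervention period", followed by a power table for refusal rates only.

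**The data.** Apart from demographics, the Aim 3 row of Table 1 lists "date of CBPC eligibility determination, date of CBPC refusal, diagnoses, triggering events". It has no enrollment status or date. Section 7 is wider: "We request the waiver for VNS Health study staff to view identification, enrollment, and refusal data". It also says the data will be used to "analyze factors associated with CBPC enrollment and refusal in multivariable statistical modeling (described below".

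**The concern.** An eligible member can be counted as enrolled, as refused, or possibly as neither: still undecided, not reached, or dead or disenrolled before deciding. The refusal rate has all eligible members in its denominator, so someone in the third group lowers it exactly as an enrollee does. If that group exists and its share changes between periods, the change in refusal is not the change in enrollment.

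At stake is the answer to the question in Aim 3. Section 10 names increased enrollment as a potential benefit of the work. A pilot that follows the plan as written can report on refusals, but it has no defined result from which to say whether more members enrolled.

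**Working it through.** **1. The plan's own figure.** Inputs from Section 9: 250 members per period, α = 0.05, pre-period refusal 80/250 = 0.32, post-period refusal 0.206 at 80% power. The test and its sidedness are not stated. A two-sided, continuity-corrected comparison of two proportions reproduces the table:

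z = [(d − 1/n)√n − 1.96√(2p̄(1−p̄))] / √(p₁(1−p₁) + p₂(1−p₂))

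With d = 0.114, n = 250 and p̄ = 0.263: z = (1.739 − 1.220)/0.617 = 0.84, so power is 0.80. The other three rows give 0.849, 0.901 and 0.948 against the stated 0.85, 0.90 and 0.95. The refusal calculation is sound.

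**2. How refusal and enrollment are linked.** Let E, R and N be the shares of eligible members who enroll, refuse, or do neither. Since E + R + N = 1,

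rise in E = fall in R − rise in N.

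The plan measures the fall in R. It gives the rise in E only if N does not change, and N is certain not to change only if it is zero in both periods. The documents neither give N nor say that it is zero.

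**3. If N is zero.** Pre-period enrollment is 1 − 0.32 = 0.68 and post-period enrollment is 1 − 0.206 = 0.794. This is the same comparison read the other way round, with the same power of 0.80.

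**4. If N is not zero.** Pre-period enrollment must then be assumed. With 32% refusing, its ceiling is 68%; the range 28% to 68% corresponds to N from 40% down to 0%. The first column of results is the 95% half-width 1.96√(2p(1−p)/250). The others apply the formula in step 1 to enrollment, with all of the 11.4 points, or half of them (5.7), becoming enrollment.

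| Assumed pre-period enrollment | Assumed N, pre-period | 95% half-width (points) | Power, all 11.4 points | Power, 5.7 points |
|---|---|---|---|---|
| 28% | 40% | 7.9 | 0.74 | 0.25 |
| 38% | 30% | 8.5 | 0.70 | 0.22 |
| 48% | 20% | 8.8 | 0.69 | 0.22 |
| 58% | 10% | 8.7 | 0.73 | 0.23 |
| 68% | 0% | 8.2 | 0.80 | 0.26 |

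The expected 95% confidence interval for the enrollment difference is about 3 to 20 points if all 11.4 points convert, and about −3 to 14 points if half do.

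**5. The cross-reference in Section 7.** Section 9 covers satisfaction and use measures, the qualitative analysis, descriptive statistics, and the pre-post refusal comparison with its power. It contains no multivariable model and no covariates, and no later section supplies them.

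**The case against.** The strongest reply is that the third group may not exist. No section mentions eligible members who neither refuse nor enroll. Section 4 already removes those whom the clinical team finds ineligible, which takes one obvious source of unresolved cases out of the denominator. If everyone left either accepts or refuses, enrollment is one minus refusal and the mismatch is only one of wording. This stands as far as it goes: the documents do not show that the group exists. They do not rule it out either, and Section 7 lists enrollment and refusal as separate data items.

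Refusal is also a sensible near-term outcome for materials used in the offer conversation, and the plan uses it consistently in Sections 3, 9 and 10. That supports keeping it primary. The missing enrollment field cannot be fully checked, because Section 3 refers to an Appendix that was not available.

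A reader might draw three stronger conclusions that the documents do not support:

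- *That an enrollment-effect analysis was announced and then left out.* The model in Section 7 concerns factors associated with both enrollment and refusal. It is not described as a test of the intervention's effect on enrollment.
- *That a significant fall in refusals with no gain in enrollment is a likely result.* It can be constructed: moving 21 members from refused to neither gives 80/250 against 59/250, with p = 0.046 on the corrected test. But 21 is the smallest shift that reaches p < 0.05 (60/250 gives p = 0.058), and the example assumes that no averted refusal becomes an enrollment. It says nothing about likelihood.
- *That enrollment cannot be tested with adequate power.* If all non-refusers enroll, power is the plan's own 0.80.

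**Conclusion.** The point holds in a conditional form. The aim concerns enrollment, the only effectiveness outcome compared is refusal, and the documents do not state the link between them. Unless the two are exact complements, the planned comparison cannot by itself support a statement about enrollment.

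The size of the problem is unknown, because the share who neither refuse nor enroll is not given. What can be bounded is how well 250 members per period would measure enrollment. In the complement case the result equals the refusal analysis. Otherwise precision is about ±8 to 9 points. Power is then about 69% to 74% if all 11.4 points convert, for assumed pre-period enrollment of 28% to 58%. If half convert, it is about 22% to 26%, for 28% to 68%. These ranges rest on assumed enrollment rates and on the two-sided corrected test that reproduces the plan's table.

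The missing model from Section 7 is a separate, clerical matter and affects both outcomes.

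**What to change.** - Keep the refusal rate as the primary endpoint. Sample size and power table do not change.
- Add CBPC enrollment status and date to the Aim 3 fields in Table 1. Section 7 already requests enrollment data.
- Report enrolled, refused and neither for both 6-month periods, with the same follow-up cut-off after the eligibility date. Otherwise the lookback period could have had longer for its decisions to be recorded.
- Report the pre-post difference in enrolled/eligible, with a 95% confidence interval, as a secondary outcome for estimation only. Base any statement about enrollment on that result.
- Separately, describe the multivariable model in Section 9 or remove the reference in Section 7.

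The cost is some wording and a slightly larger extract. The downside is an enrollment estimate that may be inconclusive. If the records show that every non-refuser enrolls, the three-way report will show it and the refusal result can be read directly as an enrollment result.

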### **Clinical Trial.**

*PC team member Recruitment.* All of the CBPC team members who present the CBPC program to CBPC-eligible individuals and FCP will be asked to use the informational materials developed as part of this project when speaking with VNS Health Total members and FCP about the CBPC program. We will work with the CBPC leadership to identify effective ways to engage CBPC team members in the intervention while minimizing potential burden. CBPC team members who deliver the intervention (i.e., use the informational materials when explaining CBPC to eligible individuals and their FCP) will be asked to complete fidelity, feasibility, and acceptability measures (e.g., End User Satisfaction Survey) at 1, 3, and 6 months into intervention implementation.

*VNS Health Total Member Recruitment.* We plan to conduct a pilot clinical trial of integrating tailored informational materials on the benefits of community-based palliative care for eligible persons based on their individualized profile as identified by a validated 12-month mortality risk algorithm. Based on recent VNS Health Total data regarding the number of individuals identified as eligible for palliative care, we expect to run the pilot clinical trial with 500 eligible individuals over an enrollment period of 12 months. This sample of 500 individuals included in the Inclusion Enrollment Table represents all individuals expected to be identified as eligible for palliative care during the study period (250 prior to intervention implementation and 250 following intervention implementation).

All data collection from VNS Health Total members for the pilot trial will be taken from existing electronic health records and remotely collected. For the pilot trial, the study team will not interact directly with palliative care-eligible individuals, or their FCP. All outcomes for VNS Health Total members will be captured through an existing data source (the VNS Health Total electronic record) under a waiver of informed consent (see below).

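### The primary refusal rate counts any eligible member not presented with CBPC as a non-refusal, and the Aim 3 extract has no presentation field to show whether that share changed between periods

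*Combined protocol and SAP*

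**What the plan says.** The all-eligible denominator appears consistently. Table 1 gives the primary endpoint as "Number and rate of CBPC refusals (denominator=number of CBPC-eligible individuals"). Section 3 (Study Design, Aim 3) has the same ratio: "We will retrospectively examine CBPC refusal rates (CBPC refusals/CBPC eligible individuals) for a 6-month lookback" period, compared with the 6 months after launch. Section 9 (Quantitative Analysis) applies it: "We assume we will see approximately 80 refusals among the 250 pre-intervention patients, for a refusal rate of" 0.32.

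Entry to the denominator is set by eligibility. Section 4 (Aim 3) includes "All VNS Health Total members who were identified as eligible for CBPC in the 6-month period prior to the introduction of the intervention", and likewise in the 6 months after. It excludes people the algorithm did not flag and people the clinical team judged ineligible. Neither list mentions whether CBPC was presented or whether the member was already enrolled.

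Presentation is a separate step, carried out with people already eligible. Section 5 (Clinical Trial) states: "All of the CBPC team members who present the CBPC program to CBPC-eligible individuals and FCP will be asked to use the informational materials". The materials act in that conversation.

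The Aim 3 record fields in Table 1 are demographics plus "date of CBPC eligibility determination, date of CBPC refusal, diagnoses, triggering events". No presentation date or status is listed. Enrollment is not listed either, although Section 7 requests access to identification, enrollment and refusal data for Aim 3.

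**The concern.** The all-eligible rate is the product of two quantities: the share of eligible members presented with CBPC, and the refusal rate among those presented. The materials are meant to change the second. The first depends on staffing, on reaching people, and on members dying or leaving the plan before a conversation takes place.

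The comparison is before-after with no concurrent control, so nothing holds the first factor constant. The error can also point the wrong way: fewer conversations after launch would lower the primary rate and look like the hypothesised benefit, although Aim 3 is about raising enrollment. More conversations after launch would hide a real effect. With no presentation field in the extract, the trial could neither detect nor rule out either case.

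**Working it through.** **Inputs from Section 9.** 250 members per period, 80 pre-period refusals (0.32), alpha 0.05, and a detectable post rate of 0.206 at 80% power (35.6% relative reduction). The sidedness of the test is not stated.

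**Reproducing the plan's table.** A two-sided test of two proportions with continuity correction, n = 250 per period, gives power 0.800, 0.849, 0.901 and 0.949 for post rates 0.206, 0.199, 0.190 and 0.178. The plan states 0.80, 0.85, 0.90 and 0.95. Without the correction, row 1 gives 0.827; one-sided and uncorrected, it gives 0.896. So the two-sided corrected test is used below, by exact binomial enumeration. That gives 0.801 for row 1, and 0.020 for a significant fall when nothing changes.

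**Assumption.** The documents do not give the unpresented share f, so a range is shown.

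**Formulas.** Refusal among those presented: c = 0.32 / (1 − f_pre). All-eligible post rate with no change in decisions: c × (1 − f_post).

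**Level.** If 10%, 20% or 30% go unpresented, 0.32 corresponds to c = 0.32/0.9 = 0.356, 0.32/0.8 = 0.400 or 0.32/0.7 = 0.457. If f = 0, c = 0.32.

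**Equal shares.** If f_post = f_pre, the post rate is 0.32 and the chance of a significant fall stays at 0.020. No spurious benefit arises.

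**Unequal shares, no change in decisions:**

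| f pre → post | Post rate | Chance of a significant fall |
|---|---|---|
| 5% → 10% | 0.303 | 0.049 |
| 10% → 15% | 0.302 | 0.052 |
| 10% → 20% | 0.284 | 0.117 |
| 10% → 30% | 0.249 | 0.385 |
| 20% → 40% | 0.240 | 0.475 |
| 0% → 10% | 0.288 | 0.100 |

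**Masking.** With f falling from 20% to 10% and a true 35.6% reduction among those presented, the post rate is 0.40 × 0.644 × 0.90 = 0.232. Power is 0.56, against 0.80 with equal shares.

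**Would a presented-only denominator be safe?** If who is presented is unrelated to who would refuse, the chance of a false fall stays at 0.019 to 0.020 in these scenarios. If it is related, it does not. Let f rise from 10% to 30% with no true effect, and let the 50 newly unpresented members be people of whom 60% would have refused. Refusals fall from 80 to 80 − 30 = 50 among 175 presented. The rate goes from 80/225 = 0.356 to 50/175 = 0.286, and the chance of a significant fall is 0.28. The all-eligible rate also drops, to 50/250 = 0.20, so neither rate is sufficient alone.

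**The case against.** The strongest reply is that the plan asks about eligible people, and its denominator matches. Aim 3 and Section 9 both frame the effect among eligible individuals, and the intervention is materials plus process within existing workflows. Refusals over all eligible is then a coherent population measure, close in spirit to intention to treat. This stands, and it is why the primary rate should be kept.

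A reader might infer that 0.32 is understated and that the denominator should be replaced by members presented. The documents do not support this. No section says that any eligible member goes unpresented. Deceased people are mentioned in Section 7, but for the planning extract on refusals, whose subjects had evidently been offered CBPC; this is not evidence of death before an offer. Re-flagging of current enrollees is possible under the Aim 3 criteria but is nowhere described. A presented-only rate also conditions on something that happens after launch and can bring its own selection, as shown above.

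A reader might also infer that presentations will fall after launch. Section 10 says that identifying and approaching previously offered people does not change, and Section 5 promises to limit burden and to check in monthly. These make a large shift less likely. They do not measure it, and the Section 10 statement covers only people offered before.

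The enrollment data named in Section 7 would help: enrolled plus refused gives everyone with a recorded decision. Undecided and unpresented members would still be indistinguishable. Slower presentation is partly a question of follow-up length, and the scenarios here do not depend on it.

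**Conclusion.** The point holds in conditional form. The denominator is all eligible members, an unpresented member counts as a non-refusal, and no listed field shows presentation. No stated figure is wrong: 80/250 = 0.32 fits the stated measure and the power table reproduces.

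The threat is a change in the share presented between periods. A 5-point rise in the unpresented share is minor (about 5% false benefit against 2%). Rises of 10 to 20 points from a 10% base are not (about 12% to 38%). A fall from 20% to 10% costs about 24 points of power. These sizes rest on assumed shares, on refusal among those presented being unchanged (or reduced by 35.6% in the masking case), and on the two-sided corrected test inferred from the plan's table. This is an inexpensive improvement that affects what a fall in refusals can be said to mean.

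**What to change.** Keep refusals over all eligible members as the primary rate. Then:

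- Add to the Aim 3 extract in Table 1 whether and when CBPC was presented, the recorded reason if it was not (for example died, left the plan, not reached, already enrolled), and enrollment.
- In Section 9, commit to reporting presented/eligible, refused/presented and enrolled/eligible for both periods beside the primary rate.
- State in advance that a fall in the primary rate will not be attributed to the materials if the share presented also fell or enrollment did not rise.
- State how members already enrolled in CBPC at the eligibility date are handled, and apply the same rule in both periods.

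**Cost.** A few more fields from records the study already plans to use, and wording in Table 1 and Section 9. Confirm that the waiver requested in Section 7 covers the presentation fields. Presentation may be poorly recorded in the lookback; if so, report how complete it is and read the primary rate with that limit. Refused/presented remains open to selection, so it is a supporting figure and not a replacement primary.
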